APPENDIX C: DOSE ESCALATION STUDY EXTENSION

Study Extension Rationale

Subjects who completed the Dose Escalation study may be followed with additional study visits through the end of the malaria season to 1) determine whether they become infected with *P. falciparum* (as detected by RT-PCR from dried blood spots collected every 2 weeks), and 2) to extend the PK analysis of CIS43LS to approximately 9 months (as determined by measuring the concentration of CIS43LS in blood samples collected every 4 weeks). The Dose Escalation component of the study had 3 dose groups (5 mg/kg, 10 mg/kg, and 40 mg/kg of CIS43LS), while the Efficacy component of the study only had 2 CIS43LS dose groups (10 mg/kg and 40 mg/kg). Following all subjects in the Dose Escalation group (including those who received 5 mg/kg of CIS43LS) will provide insight into the potential protective efficacy of a broader range of CIS43LS doses. Extending the PK analysis of subjects in the Dose Escalation group out to a total of 9 months will provide valuable information on the PK of CIS43LS in all 3 dose groups (5 mg/kg, 10 mg/kg, and 40 mg/kg) and will allow for exploratory analyses that assess the correlation between CIS43LS concentrations in blood and *P. falciparum* infection risk over a 9-month period.

Study Extension Procedures

Participants who completed the Dose Escalation study will be offered participation in the extension study visits and undergo an informed consent process (see section 10.1). Those who agree to participate will sign the extension consent and have a screening hemoglobin test. Those with hemoglobin <7 g/dL (<8 g/dL for pregnant women) will be excluded from participating in the Extension visits; those with hemoglobin ≥7 g/dL (≥8 g/dL for pregnant women) will be enrolled and begin bi-weekly Extension study visits at the MRTC clinic in Kalifabougou. At each study visit, up to 4.5 mL of blood will be collected by fingerprick or venipuncture for blood smear, Pf RT-PCR, and PK studies, as well as possible parasite genotyping in the case of a positive malaria parasite infection (see section 8.2.3). If a participant develops symptoms of malaria or other symptoms, they will be asked to return for an illness visit (see section 8.2.1). During the final extension visit, an additional 8mL CPT tube will be collected for PBMC storage, unless the subject declines.

AEs related to the blood collection procedures and all SAEs will be collected and followed through resolution.

Participants will attend bi-weekly study visits through a common end date of December 31, 2021, at which point all participants will be completed with study participation.

Compensation

Subjects will be compensated 3,000 Communauté Financière Africaine (CFA) Franc for each study visit for the time and inconvenience of participation. Payment will be provided in cash after the completion of each visit.

Subjects will be provided with transportation to and from study visits but will not receive additional reimbursement for travel.

Abbreviated Title: Anti-malaria MAb in Mali

Version Date: October 13, 2022

Additional Procedures and Processes

Refer to main protocol sections 8-10 for additional information related to safety definitions and reporting, data evaluation, and human subject protection procedures.

Abbreviated Title: Anti-malaria MAb in Mali

Version Date: October 13, 2022

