8.4.2 Documenting, Assessing, Recording, and Reporting Events

ALL AEs, including those that may appear to have a non-study cause (see “Causality” below), will be documented (e.g., on the clinical chart/progress notes/clinical laboratory record), recorded (e.g., in the study-specified CRF/research database), and reported (e.g., cumulatively from the research database, or according to protocol-specified expedited reporting mechanism) to the sponsor from the time informed consent is obtained through the timeframe specified below. At each contact with the subject, information regarding AEs will be elicited by open-ended questioning and examinations.

AEs and SAEs will generally be recorded, assessed, and reported according to the timeframes outlined in [Table 2](#).

Abbreviated Title: Anti-malaria MAb in Mali

Version Date: October 13, 2022

Table 2. Standard event recording, assessment, and reporting timeframes.

Event type	Record, assess, and report through
Related SAEs	End of subject participation in study, or if study personnel become aware thereafter
Unrelated SAEs	End of subject participation in study
Related non-serious AEs of grade 1 to 3	End of subject participation in study
All other related non-serious AEs	End of subject participation in study
Unrelated non-serious AEs	End of subject participation in study

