8.4.2.3.4 Pregnancy

Unless otherwise specified above, all pregnancies will be reported (by REDCap, or by email and SERF if REDCap is not available) to the CSO no later than the first business day following the day of study personnel awareness.

Pregnancy outcome data (e.g., delivery outcome, spontaneous or elective termination of the pregnancy) will be reported to the CSO no later than the third business day following the day of study personnel awareness (by REDCap, or by email and SERF if REDCap is not available).

Pregnancy itself is not an AE. Events that meet AE or SAE criteria in relation to pregnancy, delivery, or the conceptus/neonate (see section [8.4.1](#)) are reportable (by REDCap, or by email and SERF if REDCap is not available).

In the event of pregnancy in a study subject exposed to study agent, the following actions will be taken, with the goal of ensuring maternal and fetal well-being, in consultation with the SMM, independent safety monitor (ISM), and DSMB:

- Sample collection will continue (including participation in extension visits described in Appendix C) per guidelines below:
 - Only proceed with blood draw if subject's hemoglobin value is ≥ 8.0 gm/dL (assessed via finger prick).
 - PK samples (4 mL) will be collected according to the regular study schedule (Day 1, Day 7, Day 14, Day 28, Day 56, Day 84, Day 112, Day 140 and Day 168), plus optional extension visits.
 - The finger prick used to measure hemoglobin at the visits specified above will also be used to collect blood smears for detection of Pf infection by microscopic examination, and dried blood spots for PfRT-PCR. A venipuncture (up to 0.5 mL) may also be performed if the investigators believe that a finger prick would not provide a sufficient volume of blood to prepare dried blood spots for the PfRT-PCR assay.
 - Serum storage samples will not be drawn if a subject becomes pregnant.

Abbreviated Title: Anti-malaria MAb in Mali

Version Date: October 13, 2022

- Continue to follow for safety for the duration of the pregnancy and for a period of up to 12 months (per investigator discretion) following delivery for assessment of the neonate (see Appendix D).
- Request to unblind the subject, if applicable, AND if doing so would offer a benefit to the subject.
- Report, no later than the first business day after study personnel awareness, to the ISM and DSMB.

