APPENDIX D: PREGNANCY FOLLOW-UP

Pregnancy Follow-up Rationale

If a woman becomes pregnant during study participation, we will follow her for safety for the duration of the pregnancy and for 12 months following delivery for assessment of the neonate. In addition to the procedures described in section 8.4.2.3.4, we will perform additional research procedures to collect information regarding the delivery outcome and the health of the neonate/infant and mother over the months following delivery. This will allow an initial assessment of PK values after delivery as well as the effects of the investigational agent on pregnancy course and outcome, and infant health.

Pregnancy Follow-up Procedures

Participants who become pregnant during the study will be offered participation in the pregnancy follow-up phase and undergo an informed consent process (see section 10.1). Women who agree to participate will sign the pregnancy follow-up consent and will undergo the following assessments at the time of delivery:

- Hemoglobin measure using HemoCue
- Peripheral malaria test (RDT, blood smear, filter paper)
- Placental malaria using blood smear, filter paper
- Placental malaria histology
- PK blood draw
- AE assessment
- Breast milk to measure CIS43LS concentrations

After delivery, we will collect a breast milk sample at each of the scheduled infant visits described below.

At the infant follow-up visits during months 6, 9, and 12, 4 mL of blood will also be collected from the mother for detection of malaria and for PK analysis.

The neonate/infant and mother will undergo research assessments according to [Table 6](#).

Table 6. Schedule of assessments for mother and neonate/infant participants.

Study Month	Month 0/ Delivery	3	6	9	12	Illness Visit	ET Visit
Window (days)	+7	±7	±7	±7	±7		
Clinical Procedures/Evaluations							
Heel/finger stick (infant)	X	X	X	X	X	X	X
Cord blood collection	X						

Abbreviated Title: Anti-malaria MAb in Mali

Version Date: October 13, 2022

Study Month		Month 0/ Delivery	3	6	9	12	Illness Visit	ET Visit
Window (days)		+7	±7	±7	±7	±7		
Weight (infant)		X	X	X	X	X	X	X
Ballard assessment (infant)		X						
Apgar (infant)		X						
Length (infant)		X	X	X	X	X	X	X
Head circumference (infant)		X	X	X	X	X	X	X
Neurological assessment (infant)			X	X	X	X	X	X
Vaccination/EPI review ^a (infant)			X	X	X	X	X	X
AE assessment (mother and infant)		X	X	X	X	X	X	X
Breast milk sample (collected from mother)		X	X	X	X	X		X

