Venous blood (collected from mother)				4 mL	4 mL	4 mL	4 mL	4 mL
Laboratory Evaluations								
Test	Tube	(infant blood volume)						
PK (heel/ finger stick)	SST	50 uL	50 uL	50 uL	50 uL	50 uL		50 uL
PK (cord blood)	SST	X						
Malaria blood smear/RDT ^b	N/A	(X)	(X)	(X)	(X)	(X)	3 to 4 drops	(X)
Hemoglobin	N/A		(X)	(X)	(X)	(X)	(X)	(X)

Abbreviated Title: Anti-malaria MAb in Mali

Version Date: October 13, 2022

Abbreviations: AE, adverse event; ET, early termination; EPI, Expanded Programme of Immunization; PK, pharmacokinetics; RDT, rapid diagnostic test.

(X) indicates that no additional blood will be drawn; the test will be performed from blood collected for another evaluation listed.

^a Record vaccination information from EPI card.

^b Only performed if enough blood is available.

The month 12 visit will be the final study visit for participants; participation will be complete after this timepoint.

For both women and children, any AEs related to the blood collection procedures and all SAEs will be followed through resolution.

Compensation

Subjects will be compensated 3,000 Communauté Financière Africaine (CFA) Franc for each study visit for the time and inconvenience of participation. Mothers and neonates/newborns will each receive compensation for study visits. Payment will be provided in cash after the completion of each visit. The parent/guardian will receive the payments for the neonate/infant participants.

Subjects will be provided with transportation to and from study visits but will not receive additional reimbursement for travel.

Additional Procedures and Processes

Refer to main protocol sections [2.3.1](#), [8](#), and [10](#) for additional information related to risks, safety definitions and reporting, and human subject protection procedures.

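### Appendix C collects fewer adverse events in the dose-escalation extension than section 8.4.2 and Table 2 require, and the length of infant follow-up is stated in two ways

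*Combined protocol and SAP*

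**What the plan says.** **Main protocol.** Section 8.4.2 opens with a broad duty to document, record and report: "ALL AEs, including those that may appear to have a non-study cause". Table 2 then sets the period. Its rows for non-serious events, including "All other related non-serious AEs" and the row for unrelated ones, all run to the end of the subject's participation. Section 8.4.2.2 adds that AEs go into the research database whatever their possible relationship to the study intervention.

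**Extension.** Appendix C is narrower: "AEs related to the blood collection procedures and all SAEs will be collected and followed through resolution". It sets a common end date of December 31, 2021, "at which point all participants will be completed with study participation". It also sends the reader back to sections 8 to 10 for safety definitions and reporting. The synopsis counts the extension within subject duration.

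**Analysis.** Section 9.4.5 summarises, by dose arm, the number and percentage of subjects with at least one AE. It gives no end date for the events counted.

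**Pregnancy.** Section 8.4.2.3.4 follows the mother through pregnancy and then, after delivery, "for a period of up to 12 months (per investigator discretion" in the words of that section. Appendix D says "for 12 months following delivery for assessment of the neonate" and makes month 12 the final visit.

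**The concern.** A site running extension visits had two instructions that cannot both be followed. Under section 8.4.2, a rash or raised ALT at month 7 that the investigator judged possibly related to CIS43LS is recorded. Under Appendix C it is neither a blood-collection AE nor an SAE, so it is not.

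Two things follow. An absence of late non-serious reactions in the extension could reflect the collection rule and not the product. And because section 9.4.5 has no cut-off, one percentage per arm could combine full ascertainment to day 168 with restricted ascertainment afterwards, in whichever subjects chose to continue.

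The difference in infant follow-up is a separate matter. If the length is discretionary, how long an infant is observed may depend on how the infant is doing; if it is fixed, it should not. The plan states both.

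**Working it through.** No power or alpha figure is at issue, so the check compares the texts and then bounds the size.

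**1. Is the extension inside the Table 2 window?** Table 2 runs to the end of participation. Appendix C places that end on December 31, 2021, after the extension visits. The synopsis gives dose-escalation subjects 8 months plus about 3 months of optional extension. So yes.

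**2. Which events are treated differently?**

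| Event first seen in the extension | Section 8.4.2 and Table 2 | Appendix C |
|---|---|---|
| SAE | recorded | collected |
| Non-serious, due to blood collection | recorded | collected |
| Non-serious, related to CIS43LS | recorded | not collected |
| Non-serious, unrelated | recorded | not collected |

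The conflict lies in the last two rows. The third matters for product safety.

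**3. How much observation is affected?** At most 18 subjects (3 arms × 6). With the stated extension of about 3 months: 18 × 3/12 = 4.5 person-years. Appendix C describes PK out to about 9 months. Day 168 is 168/30.44 = 5.5 months, so the extension could add 9 − 5.5 = 3.5 months, or 18 × 3.5/12 = 5.25 person-years. Both are upper bounds, because they assume that all 18 joined.

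**4. What could it do to the summary?** With 6 subjects per arm, one subject more or less with an AE moves the arm's percentage by 1/6 = 16.7 points. It moves only if that subject had no AE before the extension.

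**5. What is not affected?** The primary safety endpoint covers 7 days after administration. The efficacy study has no such extension, so its comparisons with placebo are untouched.

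**6. Infant follow-up.** Section 8.4.2.3.4 gives 12 months as a maximum, subject to the investigator's judgement. Appendix D gives 12 months as the length, with visits at delivery and months 3, 6, 9 and 12. The first refers to the second, but the wording differs. The number of pregnancies is not stated, so the size cannot be given.

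**The case against.** The strongest defence of Appendix C is that it is the specific rule for a sampling phase. The extension has its own consent and hemoglobin screen, is offered to people who completed dose escalation, and exists to study infection and PK. Section 8.4.2 says that Table 2 applies *generally*, which leaves room for exceptions. A lighter AE burden there may be deliberate and reasonable. What stands is that a restricted rule is a permissible choice. What does not stand is that the plan makes it clearly: section 8.4.2 names no exception, Table 2 has no extension row, and Appendix C points back to section 8. Illness visits would bring some symptoms to attention, but neither Appendix C nor section 8.2.1 says that these are then recorded as AEs.

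It is also fair to say that the extension ended on December 31, 2021, while this version is dated October 13, 2022. New wording cannot recover data from those visits. That changes the remedy but leaves the inconsistency.

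A reader might go further and infer that AEs in mothers and infants also go unrecorded, or that Appendix D contradicts Table 2. The documents do not support this. Table 6 schedules an AE assessment for mother and infant at every visit, including illness and early-termination visits, and section 8.4.2.3.4 makes AEs concerning pregnancy, delivery or the neonate reportable. The similar sentence in Appendix D, "any AEs related to the blood collection procedures and all SAEs will be followed through resolution", limits only which events are followed until they resolve. Table 2 governs recording, assessing and reporting, and sets no rule on follow-up to resolution.

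**Conclusion.** The conflict between Appendix C and section 8.4.2 with Table 2 is real and can be read directly from the text. If Appendix C was applied as written, non-serious reactions to CIS43LS first seen in the extension were not recorded, whatever their true rate. The size is small: at most 18 subjects and about 4.5 person-years, in a descriptive summary, with the primary safety endpoint unaffected. The documents do not show which rule the site used, so the loss is possible and not established.

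A reader might also argue from residual exposure. Section 4.3 estimates about 90 µg/mL at 3 months and 30 µg/mL at 6 months after 10 mg/kg. That implies a half-life of 91 × ln 2 / ln 3 ≈ 57 days and roughly 10 µg/mL at 9 months. These are approximate, extrapolated figures. They show that antibody probably remains, not that late reactions occur; section 2.3.1 puts most infusion-related events within 24 hours and delayed allergic reactions typically at several days.

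The mismatch in the length of infant follow-up is a separate wording conflict of unknown size. Overall severity: minor.

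**What to change.** 1. **Reconcile Appendix C with section 8.4.2 and Table 2.** Either have Appendix C also collect non-serious AEs judged possibly, probably or definitely related to CIS43LS, or add an extension row to Table 2 that states the exclusion.
2. **State which rule was applied**, in the analysis plan and the report, since the extension is over. If it was the restricted rule, end the by-arm summary of non-serious AEs in section 9.4.5 at day 168 and report the extension's SAEs and blood-collection AEs separately.
3. **Reconcile the length of infant follow-up** between section 8.4.2.3.4 and Appendix D, so that one statement governs.

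The cost is a few sentences and one table row. No extra visits or samples are needed. Data not collected in the extension cannot be recovered, so the gain lies in correct interpretation.

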APPENDIX D: PREGNANCY FOLLOW-UP

Pregnancy Follow-up Rationale

If a woman becomes pregnant during study participation, we will follow her for safety for the duration of the pregnancy and for 12 months following delivery for assessment of the neonate. In addition to the procedures described in section 8.4.2.3.4, we will perform additional research procedures to collect information regarding the delivery outcome and the health of the neonate/infant and mother over the months following delivery. This will allow an initial assessment of PK values after delivery as well as the effects of the investigational agent on pregnancy course and outcome, and infant health.

Pregnancy Follow-up Procedures

Participants who become pregnant during the study will be offered participation in the pregnancy follow-up phase and undergo an informed consent process (see section 10.1). Women who agree to participate will sign the pregnancy follow-up consent and will undergo the following assessments at the time of delivery:

- Hemoglobin measure using HemoCue
- Peripheral malaria test (RDT, blood smear, filter paper)
- Placental malaria using blood smear, filter paper
- Placental malaria histology
- PK blood draw
- AE assessment
- Breast milk to measure CIS43LS concentrations

After delivery, we will collect a breast milk sample at each of the scheduled infant visits described below.

At the infant follow-up visits during months 6, 9, and 12, 4 mL of blood will also be collected from the mother for detection of malaria and for PK analysis.

The neonate/infant and mother will undergo research assessments according to [Table 6](#).

Table 6. Schedule of assessments for mother and neonate/infant participants.

Study Month	Month 0/ Delivery	3	6	9	12	Illness Visit	ET Visit
Window (days)	+7	±7	±7	±7	±7		
Clinical Procedures/Evaluations							
Heel/finger stick (infant)	X	X	X	X	X	X	X
Cord blood collection	X						

Abbreviated Title: Anti-malaria MAb in Mali

Version Date: October 13, 2022

Study Month		Month 0/ Delivery	3	6	9	12	Illness Visit	ET Visit
Window (days)		+7	±7	±7	±7	±7		
Weight (infant)		X	X	X	X	X	X	X
Ballard assessment (infant)		X						
Apgar (infant)		X						
Length (infant)		X	X	X	X	X	X	X
Head circumference (infant)		X	X	X	X	X	X	X
Neurological assessment (infant)			X	X	X	X	X	X
Vaccination/EPI review ^a (infant)			X	X	X	X	X	X
AE assessment (mother and infant)		X	X	X	X	X	X	X
Breast milk sample (collected from mother)		X	X	X	X	X		X
Venous blood (collected from mother)				4 mL	4 mL	4 mL	4 mL	4 mL
Laboratory Evaluations								
Test	Tube	(infant blood volume)						
PK (heel/ finger stick)	SST	50 uL	50 uL	50 uL	50 uL	50 uL		50 uL
PK (cord blood)	SST	X						
Malaria blood smear/RDT ^b	N/A	(X)	(X)	(X)	(X)	(X)	3 to 4 drops	(X)
Hemoglobin	N/A		(X)	(X)	(X)	(X)	(X)	(X)

Abbreviated Title: Anti-malaria MAb in Mali

Version Date: October 13, 2022

Abbreviations: AE, adverse event; ET, early termination; EPI, Expanded Programme of Immunization; PK, pharmacokinetics; RDT, rapid diagnostic test.

(X) indicates that no additional blood will be drawn; the test will be performed from blood collected for another evaluation listed.

^a Record vaccination information from EPI card.

^b Only performed if enough blood is available.

The month 12 visit will be the final study visit for participants; participation will be complete after this timepoint.

For both women and children, any AEs related to the blood collection procedures and all SAEs will be followed through resolution.

Compensation

Subjects will be compensated 3,000 Communauté Financière Africaine (CFA) Franc for each study visit for the time and inconvenience of participation. Mothers and neonates/newborns will each receive compensation for study visits. Payment will be provided in cash after the completion of each visit. The parent/guardian will receive the payments for the neonate/infant participants.

Subjects will be provided with transportation to and from study visits but will not receive additional reimbursement for travel.

Additional Procedures and Processes

Refer to main protocol sections [2.3.1](#), [8](#), and [10](#) for additional information related to risks, safety definitions and reporting, and human subject protection procedures.
